#### **6.6.2. EORTC QLQ-C30**

#### **Functional scales:**

- Physical functioning: (1 ((Q1+Q2+Q3+Q4+Q5)/5 1)/3) \* 100
- Role functioning: (1 ((Q6+Q7)/2-1)/3) \* 100
- Emotional functioning: (1 ((Q21+Q22+Q23+Q24)/4-1)/3) \* 100
- Cognitive functioning: (1 ((Q20+Q25)/2-1)/3) \* 100
- Social functioning: (1 ((Q26+Q27)/2-1)/3) \* 100

#### Global health status:

• Global health status/QoL: ((Q29+Q30)/2-1)/6 \* 100

#### **Symptom scales/items:**

Fatigue: ((Q10+Q12+Q18)/3-1)/3 \* 100

Nausea and vomiting: ((Q14+Q15)/2-1)/3 \* 100

• Pain: ((Q9+Q19)/2-1)/3 \* 100

Dyspnea: ((Q8-1)/3 \* 100
 Insomnia: (Q11-1)/3 \* 100

Appetite loss: (Q13-1)/3 \* 100

Constipation: (Q16-1)/3 \* 100

Diarrhea: (Q17-1)/3 \* 100

Financial difficulties: (Q28-1)/3 \* 100

Missing values will be imputed for missing items by "assuming that the missing items have values equal to the average of those items which are present" for any scale in which at least half the items are completed. A scale in which less than half of the items are completed will be treated as missing. A questionnaire will be considered as received if at least one of the 15 scales is non-missing (after imputation). All scales and single items are scored on a categorical scale and linearly transformed to 0-to-100 scales with higher scores for a functional scale representing higher levels of functioning, higher scores for the global health status/quality of life representing higher levels of global health status/quality of life, and higher scores for a symptom scale representing higher level of symptoms.

PRO endpoints relating to the EORTC QLQ-C30 are as follows:

- Change from screening in each EORTC QLQ-C30 scale
- Time to first deterioration in the EORTC QLQ-C30 global health status and physical functioning scores
- Proportion of patients with deterioration based on the EORTC QLQ-C30 global health status and physical functioning scores

Baseline and change from baseline in EORTC QLQ-C30 global health status/quality of life (QoL) composite scale data and the remaining EORTC QLQ-C30 scale data will be summarized by time point using descriptive statistics for each cohort. In addition, the percentage of patients demonstrating a clinically meaningful deterioration (defined as a 10-point change from baseline) will be presented for each scale at each assessment time point. Percentages will be based on number patients assessed at each assessment time point.

The changes values from baseline to post-baseline and shift evaluation from baseline to post-baseline will be summarized.

Time to deterioration (TTD) of PRO scores is defined as the period between PRO at screening and the first deterioration (including death). Patient who did not have post-baseline deterioration will be censored on the last date of assessment.

CC

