PRO (EQ-5D and EORTC QLQ-C30)		X					X			Evaluated at screening and as close as possible to the tumor assessment schedule: at the end of every 2 cycles (up to +2 weeks) through Cycle 4 and every 3 cycles (± 7 days) thereafter until disease progression or initiation of new anticancer therapy (whichever is first).	
Tumor assessments / scans		X					X		(X)	
Same tumor assessments/scans obtained at screening at the end of every 2 cycles (up to +2 weeks) up to Cycle 4. Thereafter tumor assessments may be performed every 3 cycles (± 7 days), or as clinically indicated, until radiologic PD or initiation of new anticancer therapy (whichever occurs first).
 
At EOT, tumor assessment must be performed if the prior scan was performed ≥ 9 weeks prior to discontinuation of treatment if the patient discontinued for reasons other than radiologic disease progression. See also Section 9.17.
 
After EOT, patients who discontinued for reasons other than radiologic disease progression should continue to receive tumor assessments every 3 cycles (± 7 days), or as clinically indicated, until radiologic disease progression or initiation of new anticancer therapy (whichever occurs first).
	

	Pre-Screening	Screening Period (Within 28 Days Prior to First Dose)	Treatment Period (1 cycle = 21 days)				Safety Follow-up		Survival Follow-up Period	Notes
			Cycle 1			Cycles ≥ 2	End of Tx (+0-7 days)	30 (± 3) days After Last		
			Day 1	Day 4 ($\pm 1d$)	Day 8 ($\pm 3d$)	Day 15 ($\pm 3d$)				
Survival status								X	After discontinuation of treatment, survival follow-up should occur every 3 months (± 2 weeks) for up to 18 months after last patient enrolled in the Phase 2 portion of the study.	
TAS-120 Dosing			—————→							Patients are required to fast for ≥ 2 hours before and 1 hour after each administration of TAS-120; patients are permitted to drink water. TAS-120 should be administered in the morning or evening, at the same time (if possible) each day. See Section 8.1.1.

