9.18. Patient-Reported Outcomes

Two Patient-Reported Outcome (PRO) instruments, EuroQol-5D measure of health-related quality of life (EQ-5D) and the European Organization for Research and Treatment of Cancer Quality of Life Questionnaire (EORTC QLQ-C30) will be used in the Phase 2 part of the study. EQ-5D is a standardized measure of health status as patient-reported outcome assessment. EORTC QLQ-C30 is an integrated system for assessing the health-related quality of life of cancer patients participating in international clinical trials. These assessments will be collected at the following time points (as close as possible to the time points when tumor assessment is performed):

- Screening within 28 days prior to Day 1 of Cycle 1.
- At the end of every 2 cycles (up to +2 weeks), up to Cycle 4.
- Following Cycle 4, at least after every 3 cycles (\pm 7 days) or as clinically indicated.
- At end of treatment (EOT)

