#### 3.2.2. Secondary Endpoints

Duration of response (DOR)

Duration of response is defined as the time from the first documented response (CR or PR) to the first documented objective progressive disease (PD) or death due to any cause.

Disease control rate (DCR)

Disease control rate is defined as the proportion of patients with objective evidence of CR, PR, or SD, except that there is no requirement for a confirmation of an SD response.

Progression-free survival (PFS)

PFS is defined as the time from the first dosing date to the date of the first documented progression or death due to any cause, whichever occurs first.

Overall survival (OS)

OS is defined as the time between the first dosing date and the date of death.

ORR, DOR, DCR and PFS endpoints will be calculated based on IRC and based on investigator assessment

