# 15 October 2020

		Screening Period	Treatment Period (1 cycle = 21 days)				Safety Follow-up		Follow-	Notes			
	Duo	Dna	Pre-	Dna	(Within 28 Days	Cycle 1			Cycles ≥2	End of Tx (+0-7 days)	days Last	-	
	Screening	Prior to First	Day				Day	1 of -7 da	(±3) er	Survival up Period			
		Dose)	1	4 (±1d)	8 (±3d)	15 (±3d)	1 (±3d)	End (+0-	30 (±3 After	on Jan			
12-Lead Electrocardiogram		x	X				X	X	X		At screening and 2 hours (±15 minutes)  after dosing on D1 of each cycle.		
Hematology and coagulation		x	x		x	X	x	X	X		Within 24 hours prior to treatment on D1 of each cycle, any time on C1D8 and C1D15, and as clinically indicated.		
Chemistry (Serum or plasma)		x	x	(X)	x	х	x	X	x		Within 24 hours prior to treatment on D1 of each cycle, any time on C1D8 and C1D15, and as clinically indicated. Additional collection for phosphorus only at C1D4.		
Urinalysis (Urine dipstick)		X	X				X	X	X				
Pregnancy test		x	x				x	X	x		Serum pregnancy test required for WOCBP at screening and end of treatment; serum or urine pregnancy test required at all other timepoints.		
Blood PK Sampling (Required)							x				Blood samples (1 mL) collected C2D1 pre-dose and at 1h and 3h (±30 min) post-dose. Additional samples collected pre-dose on C3D1 and C4D1.		
ctDNA blood samples		x						(X)			Minimum of 20 mL whole blood at screening (mandatory) and EOT (optional).		
CCI													
Prior & concomitant medications, AE assessments	х	x					→	x	x		Collect from the time main informed consent is signed through 30 days after administration of the last dose of TAS-120 or until the start of new anticancer therapy, whichever is earlier. AEs directly associated with a pre-screening procedure should be reported as described in Protocol Section 12.1		

		Screening Period	Treatment Period (1 cycle = 21 da	ıys)	Safety Follow-up	Follow-	Notes
	Pre-	(Within 28 Days	Cycle 1	Cycles ≥2	of Tx days) () days Last		
	Screening	Prior to First Dose)	Day  1	Day 1 (±3d)	End of Tx (+0-7 days) 30 (±3) days After Last	Survival up Period	
PRO (EQ-5D and EORTC QLQ-C30)		X	1 (±1d) (±3d) (±3d)	X	X	S. 1	Evaluated at screening and as close as possible to the tumor assessment schedule: at the end of every 2 cycles (up to +2 weeks) through Cycle 4 and every 3 cycles (±7 days) thereafter until disease progression or initiation of new anticancer therapy (whichever is first).

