# 15 October 2020

[figure not shown]
		Treatment Period (1 cycle = 21 days)					Safety Follow-up		Follow-	Notes	
	Pre-	Period (Within 28 Days	Cycle 1	I			Cycles ≥2	of Tx days)	days Last	o J	
	Screening	Prior to First Dose)	Day 1	4 (±1d)	8 (±3d)	15 (±3d)	Day 1 (±3d)	End o (+0-7 d	30 (±3) After	30 (±3) ds After L	
Survival status										X	After discontinuation of treatment, survival follow-up should occur every 3 months (±2 weeks) for up to 18 months after last patient enrolled in the Phase 2 portion of the study.
TAS-120 Dosing							>				Patients are required to fast for ≥2 hours before and 1 hour after each administration of TAS-120; patients are permitted to drink water. TAS-120 should be administered in the morning or evening, at the same time (if possible) each day. See protocol Section 9.1.1.

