# **5.3.** Populations for Analysis

- **Safety Population:** All patients who received at least 1 dose of TAS-120. This population will be the primary population for safety evaluation
- Efficacy Population: All Intra-hepatic cholangiocarcinoma (iCCA) patients who received at least 1 dose of TAS-120 with FGFR2 gene fusions or other FGFR2 rearrangements
- PRO Population: All patients who received TAS-120 treatment and had EQ-5D or EORTC QLQ-C30 assessment at baseline and at least one subsequent post-baseline assessment
- Per-protocol Patients (Per-Protocol Population): All treated subjects who have no relevant protocol deviations. For patients who have a relevant deviation during the study, data collected before the point of deviation can be included in the analysis preformed for this population.

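### Phase 2 SAP 6.6.2 starts PRO time to deterioration at the screening form and counts death without a time limit, so it includes pre-treatment event-free days and makes time at risk depend on later survival

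*SAP*

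**What the plan says.** Phase 2 SAP Section 6.6.2 names time to first deterioration (TTD) in QLQ-C30 global health status and physical functioning as a PRO endpoint. It sets the origin and event in one sentence: "Time to deterioration (TTD) of PRO scores is defined as the period between PRO at screening and the first deterioration (including death". The next sentence gives the only censoring rule: "Patient who did not have post-baseline deterioration will be censored on the last date of assessment".

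The surrounding provisions are:

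- **Baseline form.** Protocol 9.18 places it at "Screening within 28 days prior to Day 1 of Cycle 1". SAP Table 12 gives a window of 28 days to 1 day before dosing. No PRO form is scheduled on Cycle 1 Day 1.
- **Population.** SAP 5.3 defines the PRO population as "All patients who received TAS-120 treatment and had EQ-5D or EORTC QLQ-C30 assessment at baseline and at least one subsequent post-baseline assessment".
- **End of forms.** In Protocol Table 2 and SAP Table 1, PRO collection runs "until disease progression or initiation of new anticancer therapy (whichever is first", and there is an end-of-treatment form.
- **End of death follow-up.** SAP Table 1 says "survival follow-up should occur every 3 months (±2 weeks) for up to 18 months after last patient enrolled in the Phase 2 portion".
- **Other clocks.** SAP 3.2.2 says "OS is defined as the time between the first dosing date and the date of death". PFS there also starts at first dose.
- **PFS limits on late events.** Under Table 6, row 7, a death or progression that follows two or more missed assessments is censored at the last assessment before the gap. Footnote a sets a further limit of 21 days after last dose. Section 6.6.2 gives TTD no counterpart to either.

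**The concern.** A time-to-event clock should start when the patient becomes able to have the event, and a patient's time at risk should not depend on what happens later. Section 6.6.2 departs from both.

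At the start, an analysed patient must have been dosed and must have returned a later form. Such a patient cannot have died before dosing, and no score can have worsened before that later form. The days between the screening form and first dose are event-free by construction, yet they are added to every patient's TTD.

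At the end, death counts whenever it occurs, but survival without death is credited only up to the last form. Once forms have stopped, the patients still at risk without deterioration are those who will later die.

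With no control arm, the absolute median and curve are the whole result for this endpoint. They will be reported beside PFS and OS medians that run on a different clock.

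**Working it through.** The documents give no median, event count or sample size for TTD, so there is no plan figure to reproduce.

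**1. Origin.** Inputs are the screening window (Table 12; Protocol 9.18) and 30.4375 days per month.

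- Shortest shift: 1 / 30.4375 = 0.03 month.
- Longest shift: 28 / 30.4375 = 0.92 month.

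Moving the origin to first dose shortens each patient's TTD by that patient's own gap. If every gap were 28 days, the whole curve and its median would move by 0.92 month.

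**2. Event-free time that remains.** Entry to the PRO population needs a post-baseline form, so no event can precede it.

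- Tumour-assessment schedule, end of Cycle 2 (day 42, up to +14 days): 42 to 56 days from first dose. From screening, 42 + 1 = 43 to 56 + 28 = 84 days (1.4 to 2.8 months).
- Table 12 read literally (Cycle 2 Day 1 ± 3 days): 21 − 3 = 18 to 21 + 3 = 24 days from first dose. From screening, 19 to 52 days.

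An early end-of-treatment form can shorten either. A first-dose origin therefore removes only the pre-treatment part.

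**3. Late deaths.** Take two patients with the same forms, no deterioration, and a last form at month 6.

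| Patient | Later course | TTD record under 6.6.2 | Time at risk |
|---|---|---|---|
| A | dies at month 15 | event at month 15 | 15 months |
| B | alive at cut-off | censored at month 6 | 6 months |

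The two differ only in what happened after month 6, yet that decides whether the next 15 − 6 = 9 months count. There are two opposing effects. Patients like A enlarge the risk set until they die, which holds the curve up. They then count as events after patients like B have left, which pulls it down. The net direction cannot be read from the rule.

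**4. Illustration.** Kaplan-Meier simulation with 400,000 patients per scenario and a first-dose origin. None of these assumptions is in the documents: exponential times, uniform 18-month accrual, follow-up to 18 months after last enrolment, a final form at progression, and the PRO-population entry condition not applied. The alternative counts death only within 63 days (3 cycles × 21) of the last form. Times are in months.

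| Median time on forms | Median survival afterwards | Latent median to worsening | Median TTD, unlimited deaths | Median TTD, 63-day limit | Change | Share of SAP-rule events that are deaths >63 days after last form |
|---|---|---|---|---|---|---|
| 3.2 | 6 | 12 | 7.78 | 6.90 | −0.88 | 59.5% |
| 6 | 9 | 24 | 12.42 | 15.18 | +2.76 | 60.8% |
| 9 | 12 | 24 | 15.01 | 18.24 | +3.23 | 52.0% |
| 9 | 12 | 12 | 11.04 | 11.04 | 0.00 | 39.0% |

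A separate set of four scenarios (200 runs of 100 patients, median PFS 5 to 8 months, latent worsening 6 to 12 months, 70-day limit) gave changes of 0, +0.73, −1.71 and 0 month. Medians tend to sit on scheduled form dates (for example 210 / 30.4375 = 6.90), so some of these movements are jumps of one visit.

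**The case against.** **Low stakes.** Phase 2 is single-arm and open-label. TTD has no test or decision rule, and Protocol 12.2.2.6 plans only descriptive PRO summaries. This stands, and it limits the weight of the point. A reader might infer immortal-time bias in favour of treated patients, but there is no untreated group for that to apply to.

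**The origin is a convention.** The QLQ-C30 endpoints are changes from screening, so starting the clock at the reference measurement is internally consistent. The shift is also smaller than the 63-day interval between later forms. Both are fair. The screening form can remain the baseline score without also being the time origin, and nothing in the SAP explains why TTD differs from PFS and OS.

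**The late-death reading is inferred.** Section 6.6.2 does not mention deaths after forms have stopped. That is correct. But it includes death without limit, and those deaths are collected. If they are not meant to count, the text has to say so.

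**Section 6.6 already limits sparse data.** It sets the primary PRO timepoint at the last visit before more than half of the data are missing. That rule selects a visit. It is not tied to TTD or to deaths.

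**A death window has its own weakness.** Censoring at the last form a patient who dies later can also be informative, and any particular window is a choice. This stands, and it is the reason to keep the unlimited version as a sensitivity analysis.

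**When forms stop is less clean than Table 2 suggests.** There is an end-of-treatment form, and Protocol 9.18 states no stop at progression. This narrows the gap between last form and death for some patients but does not close it.

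**Conclusion.** The point holds, at modest weight. The origin part is explicit in the text and bounded by the documents' own figures: 1 to 28 days, at most 0.92 month per patient. The late-death part follows from three provisions read together: death counted without limit, censoring at the last form, and survival follow-up that outlasts PRO collection. It makes the risk set depend on future outcome.

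Three stronger conclusions are not supported:

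- That the death rule inflates (or deflates) the median. The simulated change ran from −0.88 to +3.23 months in one set of assumptions and from −1.71 to +0.73 in another, so neither sign nor size is established.
- That the curve cannot be interpreted at all once forms stop. The evidence shows a flawed risk set, not a total loss of meaning.
- That a first-dose origin removes all guaranteed event-free time. The wait for the first post-baseline form remains.

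ORR, DOR, PFS and OS are unaffected.

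**What to change.** In Phase 2 SAP Section 6.6.2:

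1. Measure TTD from the date of first dose, keep the screening form as the baseline score, and state that no event can occur before the first post-baseline form. That timing depends on the form schedule, so reconcile the Cycle 2 and Cycle 4 Day 1 windows in Table 12 with the end-of-cycle schedule in SAP Table 1.
2. Count death as deterioration only within a pre-stated interval of the last form, and otherwise censor at that form. One scheduled interval, 63 + 7 = 70 days, is an example. The exact value is for the sponsor to choose, and fixing it in advance is what matters. This follows the approach already used for PFS in Table 6, row 7.
3. Report the unlimited-death version as a sensitivity analysis.

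The cost is a few SAP sentences and a programming change, with no new data. The origin change makes reported TTD slightly shorter, and censoring ahead of late deaths may still be somewhat informative.

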#### 6.7.1. PK Analysis

Blood samples of TAS-120 will be collected for patient on Day 1 of Cycle 2 pre-dose, post-dose 1 hour  $\pm 0.5$  and 3 hours  $\pm 0.5$  to assess the plasma exposure at 20 mg QD. In addition, blood samples will be collected on Day 1 of Cycle 3 and Day 1 of Cycle 4 pre-dose.

A summary table and subject level listing for plasma concentration will be provided.

Concentrations in pre-dose samples will be compared among Cycle 2, Cycle 3, and Cycle 4 by analysis of variance (ANOVA) with only patients who had neither dose modification nor dose interruption. Any samples that were collected after dosing will not be used in the comparison by ANOVA. Any patient who have only one pre-dose sample will be excluded from the comparison.

# 6.8. Interim Analyses

For interim review of safety, interim analyses of safety will be performed approximately every 3 months until the formal interim analysis cut-off. These interim safety review will be performed by a Safety Review Committee (SRC). A complete description of the composition of the SRC and details on the interim analysis process will be provided in a separate safety review charter. The tables, graphs, and listings to support the interim safety analyses will be provided in the safety review charter.

In addition, a formal interim analysis of safety and efficacy will be performed when approximately 70% all treated patients had 6 months of follow-up. Two-sided 95% CI and 99% CI will both be provided for both interim and primary efficacy analysis of primary efficacy endpoint.

To facilitate discussion with health authority, additional ad-hoc analysis may be performed as deemed appropriate by the sponsor.

### 7. DEFINITIONS AND CONVENTIONS FOR DATA HANDLING

#### 7.1. Baseline Period

Baseline evaluations or events are defined as evaluations or events that occur before the date and time of first dose during study treatment.

If the onset time of event or evaluation time or dosing time is missing or not collected, the following definitions will be applied:

- Pre-treatment AEs will be defined as AEs with an onset date prior to but not including the day of the first dose during study treatment
- Baseline evaluations (laboratory tests, vital signs) will be defined as evaluations with a date on or prior to the day of first dose during study treatment

If there are multiple valid assessments, the assessment that is closest to day (and time if collected) prior to the first dose of study treatment will be used as the baseline in the analyses. If multiple assessments are collected at the same date (and time if collected), the assessment with the latest database entry date (and time if collected) will considered as baseline.

#### 7.2. Post-Baseline Period

On-treatment AEs will be defined as AEs with an onset date and time on or after the date-time of the first dose of study drug (or with an onset date on or after the day of first dose of study treatment if time is not collected or is missing). An AE will be counted as on-treatment if the event occurred within 30 days of the last dose of study treatment.

On-treatment evaluations (laboratory tests, vital signs) will be defined as evaluations taken after the day (and time, if collected and not missing) of first dose of study treatment. An evaluation will be counted as on-treatment if it occurred within 30 days of the last dose of study treatment.

